5.1.7 Follow-Up

- **Required Standard of Care MRI Evaluations:** Patients will have a post-operative MRI of brain on Day +2 (\pm 1 day), 1st-Month/Week +4 (\pm 3 days)follow-up, and 6-Month/Week +24 follow-up with and without gadolinium pending scan results, patient's clinical exam and healing of incision site.
- **First Month:** Patient will be followed in the neurosciences clinic at Froedtert Health-MCW Cancer Care Center for a minimum of once a week for four weeks following PDT as part of their postoperative standard of care for brain tumor resection. During these clinic visits, patients will have a history and physical exam including thorough neurological exam and documentation of medicines and doses administered. Interval history and physical exams will focus on identifying toxicities related to Photofrin® or the PDT procedure. Additional laboratory and imaging studies will be performed as clinically indicated.
- **After the First Month:** Many study participants will go on to receive additional anti-cancer therapy following recovery of neurosurgery during this time. Therapy dosing and schedule will also be recorded for study purposes as outlined in this protocol. Patients will be followed at a schedule to be determined by their respective treating physicians. For study purposes and as part of their routine care, patients will be evaluated from Week +1 to Year +3, as clinically indicated, without study specific follow-up time points. During this time, the study coordinator will report survival status when required for DSMC review, study progress reports, as well as FDA and IRB annual reports. This is outlined in Appendix 1. Evaluation will include a thorough history and physical, MRI of the resection area, medications and doses and laboratory evaluations deemed clinically appropriate.

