6.7 Concurrent Anticancer Therapy

Concurrent anticancer therapy not defined within this protocol, including chemotherapy, radiation therapy, immunotherapy, or biologic therapy may NOT be administered to patients receiving study drug (from Day -30 to Day +30). If anticancer therapeutics are administered to the patient during this time he or she may (1) not be permitted to begin protocol therapy, (2) be removed from protocol therapy, (3) be considered inevaluable for toxicity review and/or survival analyses.

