10.2 Sample Size and Study Duration

The sample size is based on a single-arm phase II study designed to detect an increase in the 6-month relapse-free survival rate from the historical value of 35% (treated as fixed) to 55%. With 29 subjects with known 6-month outcome, the study will have 80% power to detect such an increase at a one-sided 10% significance level. This calculation is slightly conservative, because

it does not incorporate the increase in the estimated survival rate from censored observations, thus the actual power might be slightly higher. A censoring rate of less than 5% is expected, so 30 patients will be enrolled in the study. The following table shows the estimated power of the study under various hypothetical values of 6-month relapse-free survival.

6-month RFS	Power
45%	43%
50%	64%
55%	82%
60%	93%
65%	98%

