10.3 Methods of Analysis

Survival probabilities will be estimated by using the product limit estimate technique. Overall survival and Relapse-free survival will be visualized using Kaplan-Meier plots. Greenwood's formula will be used to estimate the variance. The 6-month relapse free survival will be compared to the historical control value of 35% via a one-sided z-test at a 10% significance level.

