4. Progression will be defined by any of the following: > 25% increase in sum of the products of perpendicular diameters of enhancing lesions compared with the smallest tumor measurement obtained either at baseline (if no decrease) or best response, on stable or increasing doses of corticosteroids; significant increase in T2/FLAIR nonenhancing lesion on stable or increasing doses of corticosteroids compared with baseline scan or best response after initiation of therapy not caused by comorbid events (e.g., radiation therapy, demyelination, ischemic injury, infection, seizures, postoperative changes, or other treatment effects); any new lesion; clear clinical deterioration not attributable to other causes apart from the tumor (e.g., seizures, medication adverse effects, complications of therapy, cerebrovascular events, infection, and so on) or changes in corticosteroid dose; failure to return for evaluation as a result of death or deteriorating condition; or clear progression of nonmeasurable disease.

These criteria are published and currently accepted in the neuro-oncology community⁵⁸. The imaging interpretation will be completed by a board certified neuro-radiologist, while the neurological outcome/status will be assessed by a board certified neurologist/neuro-oncologist.

PDT Phase II Trial – Glioma Tumors In Adults

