13.3.4 Safety Monitoring and Stopping Guidelines

To ensure the safety of patients on study, SAEs will be reported by 4 Weeks post PDT as defined in section 13.3.1 or section 13.3.2. The 6-month relapse free survival status will be determined based on radiological assessment as defined by section 11 and standard of care medical exam carried out at Week +24. Expected enrollment is 30 patients over the course of 3 years. The stopping guidelines are summarized in the table below.

Table: Stopping Guideline for Dose Limiting Toxicities or 6-month Relapse Free Survival

Number of patients (n)	Stopping boundary (x)
1-6	2
7-12	3
13-18	4
19-30	5

** Stopping guideline is triggered if $\geq x$ patients out of n experience a SAE with attribution to the protocol*

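### Section 6.7 lets a treated patient given other anticancer therapy by Day +30 be dropped from the survival analyses at open discretion, and section 10 defines no analysis population that prevents it

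*Combined protocol and SAP*

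**What the plan says.** Section 6.7 sets the restriction: "Concurrent anticancer therapy not defined within this protocol, including chemotherapy, radiation therapy, immunotherapy, or biologic therapy may NOT be administered" from Day -30 to Day +30. The consequence follows: "If anticancer therapeutics are administered to the patient during this time he or she may" be refused protocol therapy, be taken off it, or "be considered inevaluable for toxicity review and/or survival analyses". The section does not say which consequence applies when, who decides, or by what date.

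Section 10 does not settle it:

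- 10.2 sizes the trial on patients whose outcome is known: "With 29 subjects with known 6-month outcome, the study will have 80% power to detect such an increase".
- 10.3 gives the product-limit estimator, Greenwood variance and the test: "The 6-month relapse free survival will be compared to the historical control value of 35% via a one-sided z-test". It names no population.
- 10.4 mentions later therapy only for the secondary objectives, and only after a sustained objective response.

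Section 9.1 keeps patients who leave protocol therapy in follow-up until they are off study, but does not say that they stay in the analysis.

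On what can be known early, 5.1.7 has patients seen "for a minimum of once a week for four weeks following PDT" and requires an MRI at Week +4, with a 3-day tolerance. Section 11.3 counts as progression, among other things, "clear clinical deterioration not attributable to other causes apart from the tumor".

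**The concern.** The trial is open-label with one arm, and its primary result is one rate set against a fixed 35%. No comparator would share a selection effect, so who is counted matters directly.

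A patient who progresses in the first month is a natural candidate for prompt salvage therapy. If that therapy starts by Day +30, the same event that makes the patient a failure also opens the discretion to remove the patient. Because no deadline is set, the decision can be taken when the outcome is already known. Removing such failures raises the estimated 6-month RFS. Removing patients without progression who start other therapy early lowers it.

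The part of the window before PDT is not at issue, since a breach there can be seen before injection. The concern is with patients already treated.

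**Working it through.** **1. The plan's own figure.** Inputs from 10.2: null rate 35%, alternative 55%, one-sided 10% level, 29 patients with known outcome. With X binomial(29, p) and success at X ≥ 14, the level at p = 0.35 is 0.0978. Power at 45, 50, 55, 60 and 65% is 0.431, 0.644, 0.820, 0.929 and 0.979. This reproduces the table in 10.2 (43, 64, 82, 93, 98%). The sample size is not in dispute.

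**2. Can failure be seen inside the window?** Week +4 is Day 28. With 3 days either way the MRI falls on Day 25 to 31 counted from injection, or Day 26 to 32 counted from PDT. A scan-detected failure can therefore precede Day +30, by about five days at most. The weekly visits and the clinical-deterioration limb of 11.3 allow earlier recognition.

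**3. What exclusion would do.** The documents give no rate of early other therapy, so the number excluded, k, is an assumption. Take true RFS 35%, no censoring and the 10.3 test. Without censoring, Greenwood's variance is p̂(1 − p̂)/n, so z = (p̂ − 0.35)/√[p̂(1 − p̂)/n], and the test rejects if z > 1.2816.

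The smallest rejecting count at each analysed n is:

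| n analysed | count that rejects | z | next lower count | z |
|---|---|---|---|---|
| 30 | 15 | 1.643 | 14 | 1.281 (1.2809, just short) |
| 29 | 14 | 1.431 | 13 | 1.064 |
| 28 | 14 | 1.587 | 13 | 1.213 |
| 27 | 13 | 1.367 | 12 | 0.988 |
| 26 | 13 | 1.530 | 12 | 1.141 |

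If k failures are removed from N treated, the number of successes X stays binomial(N, 0.35) but is judged against the threshold for n = N − k:

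| failures excluded | from N = 29 | from N = 30 |
|---|---|---|
| 0 | P(X ≥ 14) = 9.8% | P(X ≥ 15) = 6.5% |
| 1 | P(X ≥ 14) = 9.8% | P(X ≥ 14) = 12.6% |
| 2 | P(X ≥ 13) = 17.9% | P(X ≥ 14) = 12.6% |
| 3 | P(X ≥ 13) = 17.9% | P(X ≥ 13) = 22.0% |

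**4. How much is discreteness?** Dropping one patient from 30 regardless of outcome gives n = 29 and 9.8%, so much of the step from 6.5% to 12.6% comes from the coarse threshold. The form of test matters too:

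- An exact binomial test needs 14, not 13, at n = 27. From 29 patients with two failures excluded it therefore stays at 9.8%, and it reaches 17.9% only with three.
- From 30 patients with three excluded, the exact test gives 12.6%, not 22.0%.
- A z-test with null variance from 30 gives 12.6% for zero to two excluded and 22.0% for three.

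**5. The other direction.** Suppose non-failures are excluded instead. From 29, one excluded requires X − 1 ≥ 14 and two require X − 2 ≥ 13. Both mean X ≥ 15, or 4.8%. From 30, one gives X ≥ 15 (6.5%) and two give X ≥ 16 (3.0%).

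**The case against.** The best case against the point is that the route is narrow and runs through a protocol breach. Other therapy is barred to Day +30, and 5.2.2 allows it only from 1 month after PDT. A scan-detected failure leaves only a few days to start barred treatment. Appendix 1 schedules neither disease evaluations nor recording of other anticancer therapy before Week 5.

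The clinical route is also hard to use. Section 11.3 requires deterioration not due to treatment complications or steroid changes, and 13.3.2 notes that many patients have neurological changes straight after surgery that mostly improve within the month. Section 13.3.4 points to imaging: "The 6-month relapse free survival status will be determined based on radiological assessment as defined by section 11", together with the Week +24 examination. In addition, 9.1 keeps such patients in follow-up, the reports to the safety committee list each patient's outcome, and a documented early failure arguably has a known 6-month outcome in the sense of 10.2.

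All of this stands as a limit on size. It does not remove the permission. History, neurological examination and MRI are scheduled before Week 5, so early failure can be seen. Follow-up and listings make exclusions traceable but do not decide who is in the primary rate.

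A reader might go further and infer that the plan biases RFS upward, or that one excluded failure doubles the false-positive rate. The documents support neither. Exclusion is permitted, not prescribed, and it can act in either direction. The apparent doubling appears only from 30 patients with the Greenwood z-test; from the planned 29, one excluded failure changes nothing.

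**Conclusion.** The point holds as an undefined exclusion rule, not as a demonstrated bias. Followed as written, the plan permits outcome-dependent removal of treated patients from its single primary rate, and no other section restores them.

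Under the stated assumptions (true RFS 35%, no censoring, planned z-test), one excluded failure among the planned 29 is harmless. Two or three would take the false-positive rate from 9.8% to 17.9%, or three would do so under an exact test. How many patients would be affected, and whether failures or non-failures would predominate, cannot be derived from the documents. This is a cheap improvement, worth making before outcomes are seen. The sample size and stated power are unaffected.

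**What to change.** In 6.7, delete the words that extend inevaluability to survival analyses.

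In 10.3, add: the primary RFS analysis and the survival analyses include every patient who met eligibility as confirmed at registration and received Photofrin and PDT, regardless of when other anticancer therapy starts, with failures counted as they occur. Tying eligibility to registration stops the histology review planned in 10.4 from reopening the population later.

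List the patients given other anticancer therapy by Day +30. Excluding them, and counting them as failures, should be sensitivity analyses only.

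The cost is a wording amendment and two short analyses. The Week +24 MRI and three-year follow-up are already planned. The downside is that early other therapy may itself delay progression in patients who stay in the primary estimate; the two sensitivity analyses would show how far that matters.

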6.8 Other Investigational Agents

PDT Phase II Trial – Glioma Tumors In Adults

[figure not shown]
Other investigational agents not specified in this protocol may NOT be given while the patient is on protocol therapy, or during the first month follow-up for toxicity review.

7.0 INVESTIGATIONAL DRUG AND DEVICE INFORMATION

7.1 Photofrin® (porfimer sodium, 75 mg) for Injection

7.1.1 Description

Photofrin® (porfimer sodium) for Injection is a photosensitizing agent used in the photodynamic therapy (PDT) of tumors and of high-grade dysplasia (HGD) in Barrett's esophagus (BE). Following reconstitution of the freeze-dried product with 5% Dextrose Injection (USP) or 0.9% Sodium Chloride Injection (USP), it is injected intravenously. This is followed 40–50 hours later by illumination of the tumor or HGD in BE with laser light (630 nm wavelength). Photofrin® is not a single chemical entity; it is a mixture of oligomers formed by ether and ester linkages of up to eight porphyrin units. It is a dark red to reddish brown cake or powder. Each vial of Photofrin® contains 75 mg of porfimer sodium as a sterile freeze-dried cake or powder. Hydrochloric Acid and/or Sodium Hydroxide may be added during manufacture to adjust the pH to within 7.2 – 7.9. There are no preservatives or other additives. The structural formula below is representative of the components present in Photofrin®.

7.1.2 Pharmacology

The cytotoxic and antitumor actions of Photofrin® are light and oxygen dependent. Photodynamic therapy with Photofrin® is a two-stage process. The first stage is the intravenous injection of Photofrin®. Clearance from a variety of tissues occurs over 40-72 hours, but tumors, skin, and organs of the reticuloendothelial system (including liver and spleen) retain Photofrin® for a longer period. Illumination with 630 nm wavelength laser light constitutes the second stage of therapy. Tumor selectivity in treatment occurs through a combination of selective retention of Photofrin® and selective delivery of light. Cellular damage caused by Photofrin® PDT is a consequence of the propagation of radical reactions. Radical initiation may occur after Photofrin® absorbs light to form a porphyrin excited state. Spin transfer from Photofrin® to molecular oxygen may then generate singlet oxygen. Subsequent radical reactions can form superoxide and hydroxyl radicals. Tumor death also occurs through ischemic necrosis secondary

to vascular occlusion that appears to be partly mediated by thromboxane A2 release. The laser treatment induces a photochemical, not a thermal, effect. The necrotic reaction and associated inflammatory responses may evolve over several days.

7.1.3 Pharmacokinetics

Following a 2 mg kg^{-1} dose of porfimer sodium to 4 male cancer patients, the average peak plasma concentration was $15 \pm 3 \text{ mcg/mL}$, the elimination half-life was $250 \pm 285 \text{ hours}$, the steady-state volume of distribution was $0.49 \pm 0.28 \text{ L kg}^{-1}$, and the total plasma clearance was $0.051 \pm 0.035 \text{ mL min}^{-1} \text{ kg}^{-1}$. The mean plasma concentration at 48 hours was $2.6 \pm 0.4 \text{ mcg mL}^{-1}$. The influence of impaired hepatic function on Photofrin® disposition has not been evaluated.

Photofrin® was approximately 90% protein bound in human serum, studied in vitro. The binding was independent of concentration over the concentration range of $20\text{--}100 \text{ mcg mL}^{-1}$.

The pharmacokinetics of Photofrin® was also studied in 24 healthy subjects (12 men and 12 women) who received a single dose of 2 mg kg^{-1} Photofrin® given via the intravenous route. The serum decay was bi-exponential, with a slow distribution phase and a very long elimination phase. The elimination half-life was $415 \pm 104 \text{ hours}$ ($17 \pm 4.3 \text{ days}$). C_{\max} was determined to be $40 \pm 11.6 \text{ mcg/mL}$ and AUC_{inf} was $2400 \pm 552 \text{ mcg} \times \text{hour mL}^{-1}$. Women had a lower C_{\max} and a higher AUC. The clinical significance of these differences is unknown. T_{\max} was approximately 1.5 hours in women and 0.17 hours in men. At the time of intended photoactivation 40-50 hours after injection, the pharmacokinetic profiles of Photofrin® in men and women were similar.

7.1.4 Drug Interactions

There have been no formal interaction studies of Photofrin® and any other drugs. However, it is possible that concomitant use of other photosensitizing agents (e.g., tetracyclines, sulfonamides, phenothiazines, sulfonylurea hypoglycemic agents, thiazide diuretics, griseofulvin, and fluoroquinolones) could increase the risk of photosensitivity reaction.

Photofrin® PDT causes direct intracellular damage by initiating radical chain reactions that damage intracellular membranes and mitochondria. Tissue damage also results from ischemia secondary to vasoconstriction, platelet activation and aggregation and clotting. Research in animals and in cell culture has suggested that many drugs could influence the effects of PDT, possible examples of which are described below. There are no human data that support or rebut these possibilities.

Compounds that quench active oxygen species or scavenge radicals, such as dimethyl sulfoxide, β -carotene, ethanol, formate and mannitol would be expected to decrease PDT activity. Preclinical data also suggest that tissue ischemia, allopurinol, calcium channel blockers and some

prostaglandin synthesis inhibitors could interfere with Photofrin® PDT. Drugs that decrease clotting, vasoconstriction or platelet aggregation, e.g., thromboxane A₂ inhibitors, could decrease the efficacy of PDT. Glucocorticoid hormones given before or concomitant with PDT may decrease the efficacy of the treatment.

7.1.5 Carcinogenesis, Mutagenesis, Impairment of Fertility

No long-term studies have been conducted to evaluate the carcinogenic potential of Photofrin®. In vitro, Photofrin® PDT did not cause mutations in the Ames test, nor did it cause chromosome aberrations or mutations (HGPRT locus) in Chinese hamster ovary (CHO) cells. Photofrin® caused < 2-fold, but significant, increases in sister chromatid exchange in CHO cells irradiated with visible light and a 3-fold increase in Chinese hamster lung fibroblasts irradiated with near UV light, Photofrin® PDT caused an increase in thymidine kinase mutants and DNA-protein cross-links in mouse L5178Y cells, but not mouse LYR83 cells. Photofrin® PDT

Pregnancy Category C: Porfimer sodium has been shown to have an embryocidal effect in rats and rabbits when given in doses 0.64 times the recommended human dose on a [mg m⁻²] basis. Porfimer sodium given to rat dams during fetal organogenesis intravenously at 0.64 times the clinical dose on a [mg m⁻²] basis for 10 days caused no major malformations or developmental changes. This dose caused maternal and fetal toxicity resulting in increased resorptions, decreased litter size, delayed ossification, and reduced fetal weight. Porfimer sodium caused no major malformations when given to rabbits intravenously during organogenesis at 0.65 times the clinical dose on a [mg m⁻²] basis for 13 days. This dose caused maternal toxicity resulting in increased resorptions, decreased litter size, and reduced fetal body weight.

Porfimer sodium given to rats during late pregnancy through lactation intravenously at 4 [mg m⁻² per day] (0.32 times the clinical dose on a [mg m⁻²] basis) for at least 42 days caused a reversible decrease in growth of offspring. Parturition was unaffected.

There are no adequate and well-controlled studies in pregnant women. Photofrin® should be used during pregnancy only if the potential benefit justifies the potential risk to the fetus.

Nursing Mothers: It is not known whether this drug is excreted in human milk. Because many drugs are excreted in human milk and because of the potential for serious adverse reactions in nursing infants from Photofrin® women receiving Photofrin® must not breast feed.

Pediatric Use: Safety and effectiveness in children have not been established.

Use in Elderly Patients: Approximately 70% of the patients treated with PDT using Photofrin®

in clinical trials were over 60 years of age. There was no apparent difference in effectiveness or safety in these patients compared to younger people. Dose modification based upon age is not required.

7.1.6 Photofrin® Administration

Photofrin® should be administered as a single slow intravenous injection over 3 to 5 minutes at 2.5 mg kg⁻¹ body weight. Reconstitute each vial of Photofrin® with 31.8 mL of either 5% Dextrose Injection (USP) or 0.9% Sodium Chloride Injection (USP), resulting in a final concentration of 2.5 mg mL⁻¹. Shake well until dissolved. Do not mix Photofrin® with other drugs in the same solution. Photofrin® reconstituted with 5% Dextrose Injection (USP) or with 0.9% Sodium Chloride Injection (USP), has a pH in the range of 7 to 8. Photofrin® has been formulated with an overage to deliver the 75 mg labeled quantity. **The reconstituted product should be protected from bright light and used immediately.** Reconstituted Photofrin® is an opaque solution, in which detection of particulate matter by visual inspection is extremely difficult. Reconstituted Photofrin®, however, like all parenteral drug products, should be inspected visually for particulate matter and discoloration prior to administration whenever solution and container permit. Precautions should be taken to prevent extravasation at the injection site. If extravasation occurs, care must be taken to protect the area from light. There is no known benefit from injecting the extravasation site with another substance.

